4.4 Withdrawal of Subjects

4.4.1 When and How to Withdraw Subjects

Subject Withdrawal Criteria

- The end of the trial for a patient will be defined for this study as (1) completion of the final 24 week evaluation, (2) death, (3) withdrawal of consent, (4) if the patient is lost to follow-up at 12 weeks clinic visit, the date of the patient's last visit for which data is available.
- Patients may be withdrawn from this trial for the reasons provided below:

Withdrawal for Adverse Event

- A patient who experiences an adverse event during the study drug administration that the Investigator judges to be related to the study drug and poses a significant risk to the patient will have the study drug discontinued. All scheduled data will be collected and the patient will be included in all safety analyses.

Withdrawal of Consent

- Patients for whom Informed Consent is withdrawn will have study drug discontinued (if the decision occurs during the study period). No further data collection will be done without written consent for follow-up data collection. All available data on these patients will be included in the safety analyses.
- Investigator Decision to Withdraw Patient Should the Investigator determine that it is in the best interest of a patient to be withdrawn from the trial, the drug will be immediately discontinued (if the decision occurs during the study period). All scheduled data deemed appropriate by the Investigator will be collected and the patient will be included in all safety analyses.
- Pregnancy; If a subject's pregnancy test is positive at 12 weeks, subject will be discontinued from further study participation and any dispensed study medication will be retrieved from the subject. Subject and child will be followed for potential adverse effects of study drug dosing.

4.4.2 Data Collection and Follow-up for Withdrawn Subjects

Even though a subject has withdrawn from the study, it may be important to collect some follow-up or survival data on such subjects throughout the protocol defined follow-up period. Such data is

important to the integrity of the final study analysis since early withdrawal could be related to the safety profile of the study drug. If a subject withdraws consent to participate in the study, for subject safety reasons, attempts should be made to obtain permission to collect follow up information whenever possible.

4.5 Replacement of Discontinued or Withdrawn Subjects

Subjects who discontinue or are withdrawn prior to completing twenty-four (24) weeks of treatment will be replaced, to achieve a target of ten subjects completing 24 weeks of dosing with study medication. The number replaced may be limited to the available inventory of (+) Epicatechin capsules.

5 Study Drug

5.1 Description

(+) EPI will be manufactured by Syngene Corporation in Bangalore, India for Cardero Therapeutics and provided without charge to study subjects. The drug product will be provided to Mayo Clinic as 25mg gelatin capsules, packaged in 42 capsules per high density polyethylene bottle.

5.2 Treatment Regimen

The starting total daily dose will be 75 mg per day (one 25mg capsule taken TID) Dose escalation for some subjects, as described above, will occur at 12 weeks to 150mg total daily dose (two, 25mg capsules taken TID).

Starting Dose	Dispense 12 week supply + 2 weeks overage @ BL visit	Increase Dose at 3 months (for some subjects)	Dispense 12 week supply + 2 weeks overage at 12 week Clinic Visit	Total # Bottles (& caps) Dispensed to each Subject
75 mg/day one cap TID 3 caps/day	7 bottles of 42 (294 caps)	150 mg/day two caps TID 6 caps per day	7 bottles of 42 caps (294 caps) OR escalated dose: 14 bottles of 42 caps (588 caps)	14 bottles (588 caps) ----- 21 bottles (882 caps) Escalated dose

5.3 Preparation and Administration of Study Drug

- The study drug will be shipped to, stored by and dispensed from the Mayo Clinic Out-Patient Research Pharmacy located in the [REDACTED]
- The study drug will be dispensed to subject/LAR, labeled to be taken orally as described in section 5.2 above.
- Certificates of Analysis and clinical supply expiry date extensions as provided by Cardero Therapeutics, based on ongoing, concurrent stability studies, should be emailed to [REDACTED]

5.4 Subject Compliance Monitoring

Study medication will be dispensed as part of the Baseline and 3 month study visits at Mayo Clinic, to be taken home with the subject. A dosing and adverse event diary will be provided to the subjects, who will be asked to record the dates/times of medication intake and any unusual symptoms. The subjects will be asked to bring their diary and the previously dispensed bottles (empty, partial and unused) to the 3 month visit for review by study staff. Parents or guardians of participants younger than 18 years of age will be asked to supervise and/or provide the medication to their child and ensure the diaries are completed.

In addition to the dosing diary, the subjects/LARs will be contacted periodically between on-site visits to assess doses are being taken as prescribed.

A count of capsules returned at the 3 month visit will be performed by a study team member/pharmacy, and the number of returned capsules and compliance will be documented.

The blood levels of (+)-EPI will be measured subsequent to the visits to provide the most accurate measure of dosing compliance.

If it is determined by study staff by review of diary, returned amounts and interview that the subject did not take 50% or greater of the daily dose for 3 days in any given week, the subject will be asked to become compliant. If it is determined by the above criteria to be non-compliant a second time, the subject will be dropped from the study.

Completed dosing diaries will be retained with the site's study source documents.

5.5 Prior and Concomitant Therapy

All concomitant medications will be allowed and at the time of enrollment and through study period will be recorded and current medications will be recorded at each clinical follow-up.

5.6 Packaging

25 mg capsules of open-label study medication will be packaged 42 capsules per bottle. The bottles will be subsequently labeled by the Research Pharmacy for each subject, based on a written prescription by a Study Investigator. A 3 month supply will be dispensed at the Baseline visit and again at the 3 month visit, as specified in Section 3.1. An overage amount (2 week supply) will be dispensed to allow for flexibility in visit scheduling.

In addition to dosing directions, the bottles shall bear a label with the statement "*Caution: New Drug--Limited by Federal (or United States) law to investigational use.*"

5.7 Masking/Blinding of Study

Not applicable; the study medication will be open label.

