ST2	Suppressor of tumorigenicity 2
TID	Ter in die (three times a day)

Study Summary

Title	A Phase II, Open Label Prospective Single Center Drug Study Evaluating the Safety and Efficacy of (+)-Epicatechin in Subjects with Friedreich’s Ataxia
Running Title	Safety and Efficacy of (+)-Epicatechin in Friedreich’s Ataxia
Protocol Number	15-006845
Phase	Phase II
Methodology	This is an open label, single center, prospective phase II drug trial to assess the safety and efficacy of (+)-EPI in the treatment of Friedreich’s Ataxia. Subjects will be evaluated at outpatient clinic visit appointments and interested qualified subjects will be consented and offered participation in this trial. Once consent has been obtained, baseline values will be established and subjects will begin treatment and follow-up over a 24 week period. Clinical and biochemical parameters will be assessed at baseline and at 12 and 24 weeks after initiation of treatment.
Overall Study Duration	Two years estimated to complete enrollment
Subject Participation Duration	24 weeks
Single or Multi-Site	Single center
Objectives	
Primary: To assess the safety and clinical efficacy from neurological, cardiac and metabolic evaluations of patients before and after treatment.
 
Secondary: To assess (i) up-regulation of relevant mitochondrial proteins (frataxin and ETC complexes I-V) and (ii) reduction of urine F2-isoprostane, before and after treatment.
 
Exploratory: To assess myocardial oxygenation by Blood Oxygenation Level Dependent (BOLD) sequence cardiac MRI, and myocardial perfusion index by Regadenoson-stress-perfusion cardiac MRI, before and after treatment as non-invasive, more sensitive endpoints for future studies.
 
To investigate neuroimaging biomarkers of disease progression including spinal cord and cerebellar volumetry, Diffusion Tensor Imaging (DTI), and Magnetic Resonance Spectroscopy (MRS).

Number of Subjects	10 subjects

Diagnosis and Main Inclusion Criteria	Study participants between the ages of ≥ 10 and ≤ 50 must have a confirmed diagnosis of Friedreich's Ataxia with disease duration ≤ 7 years and at least one affected organ system (cardiac or neurological)
Study Product, Dose, Route, Regimen	(+)-Epicatechin 25mg capsules will be administered orally TID for 24 weeks, with dose escalation to 50mg TID at 3 months for subjects not showing improvement.
Duration of Administration	24 weeks
Reference therapy	No reference therapy

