Telephone calls between baseline and 3 month on-site visits: The subjects/LAR will be contacted by study staff approximately every 15 days to assess progress, symptoms and dosing compliance. If it appears subject is experiencing adverse changes and the Investigator feels an on-site visit is warranted, the subject will be asked to come in for an interim clinic visit.

Visit 2: Week 12 (+/- 1 week)

At Visit 2, the participant will undergo a physical exam and FARS scoring. Medical history, changes to concurrent medications, adverse event diary and dosing will be reviewed and additional diaries dispensed, as needed. A physical examination will be conducted. Dosing of (+)- EPI will be adjusted depending on the performance of the 8m timed walk completed through the FARS assessment and/or cardiac assessment via MRI. If the participant shows improvement (as defined in section 3.1) compared to baseline in composite score, including the 8m timed walk or cardiac function by MRI, the medication dosage will remain the same. If the participant shows no improvement or worsening compared to baseline, the (+)- EPI dose will be increased. Additional investigations include:

- Physical Examination, Vitals, Blood Pressure
- Drug level analysis of (+)- EPI in blood
- FARS Assessment
- Blood chemistry
 - Serum BNP, calcium, cardiac troponin I, CBC, ceruloplasmin, creatinine with eGFR, frataxin, , hemoglobin A1C, iron, mitochondrial complex I-V, potassium, PT/PTT, sodium, and ST2, triglycerides, and liver panel (ALT, AST, and Alkaline Phosphatase)
- Cardiac MRI with BOLD
- Urine pregnancy test

Telephone calls between 3 month and 6 month on-site visits: The subjects/LAR will be contacted by study staff approximately every 15 days to assess progress, symptoms and dosing compliance. If it appears subject is experiencing adverse changes and the Investigator feels an on-site visit is warranted, the subject will be asked to come in for an interim clinic visit.

Visit 3: Final Evaluation- Week 24 (+/- 1 week)

At the final visit, the participant will undergo a physical exam and neurological/cardiac assessments. Changes in symptoms and any concurrent medications will be assessed and the dosing/adverse event diary will be reviewed and collected/retained. Final investigations include:

- Physical Examination, Vitals, Blood Pressure FARS Assessment
- Urine analysis: F2-isoprostane
- Blood sample(s)
 - Analysis of (+)- EPI drug level and follistatin/myostatin levels

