3.2 Primary Study Endpoints

Neurological:

- Change from baseline score using Friedreich's Ataxia Rating Scale (FARS Assessment) tool at 12 and 24 weeks.
- Changes in spinal cord fractional anisotropy, based on axial DTI measurements prescribed at the C1, T1, and L1 levels at 24 weeks.

Cardiac:

- Changes in Cardiac MRI from baseline to 12 and 24 weeks:
 - Left ventricular structural and functional characteristics (systolic function by ejection fraction and systolic strain, diastolic function, LV mass to determine ventricular hypertrophy and degree of heart failure, myocardial fibrosis by late gadolinium enhancement).
- Changes in Echocardiogram from baseline to 24 weeks:
 - Left ventricular mass, volumes, systolic and diastolic function, and strain.
- Changes in Electrocardiogram from baseline to 24 weeks to assess for electrophysiological improvement of the myocardium.
- Changes in biomarkers for heart failure and hypertrophy (ST2, BNP, Cardiac Troponin) from baseline, at 12 weeks and 24 weeks.

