- Upregulate endogenous antioxidant mechanisms (SOD2, catalase) controlled by the Nrf2 pathway [18] which is inhibited in FA cells [46]; this may enhance FA cells resistance to iron-catalyzed oxidative damage.
- Promote fatty acid oxidation through regulation of SIRT3 signaling [9, 19] which is inhibited in FA cardiac cells and believed to contribute to the FA cardiomyopathy [47].
- Enhance insulin sensitivity through the PI3K/AKT pathway and AMPK [10] which may further improve metabolic dysfunction in FA.
- Through the basic mechanisms described above, (+)-EPI treatment will ultimately prevent further loss of neuronal, cardiac, and pancreatic β cells and thereby delay or arrest FA neurodegeneration, cardiomyopathy and diabetes.

Statistical analysis approach for secondary endpoint will be similar to approach listed above for primary endpoints.

Interim Analysis

Interim analysis will be performed after 50% i.e. 5 out of 10 patients have completed 12 week follow-up. Sample size at interim analysis is too small to reach required p-value for stopping decision based on O'Brien Fleming Stopping boundary criterion (i.e. p-value less than 0.0054 for stopping at interim analysis). Thus decision of stopping versus continuation of the study will be based on clinical significance rather than statistical significance. We will consider treatment to be efficacious if the cardiac MRI, neurologic MRI, and /or FARS score improve by greater than 30% at 3 months.

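### No masking of image readers is specified for the primary imaging endpoints, although visit order can be masked on stored scans even when the drug is open label

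*Combined protocol and SAP*

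**What the plan says.** The protocol's only masking provision is Section 5.7, under Study Drug: "Not applicable; the study medication will be open label". Neither it nor any other section says who reads the images, or whether reads are masked, batched, duplicated or centralised.

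The Study Summary describes the design: "This is an open label, single center, prospective phase II drug trial", with "No reference therapy" as comparator. Section 7.2 tests change from baseline with a paired t-test or Wilcoxon signed rank test.

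Section 3.2 lists these imaging measures as primary:

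- "Changes in spinal cord fractional anisotropy, based on axial DTI measurements prescribed at the C1, T1, and L1 levels at 24 weeks"
- "Changes in Cardiac MRI from baseline to 12 and 24 weeks" (left ventricular structure and function, strain, fibrosis)
- "Changes in Echocardiogram from baseline to 24 weeks" (left ventricular mass, volumes, function, strain)

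Spinal cord and cerebellar volumes are secondary (Section 3.3).

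Cardiac MRI is also used while the trial runs. At Visit 2 (Section 3) the dose is adjusted "depending on the performance of the 8m timed walk completed through the FARS assessment and/or cardiac assessment via MRI", by comparison with baseline. Section 7.2 adds: "Interim analysis will be performed after 50% i.e. 5 out of 10 patients have completed 12 week follow-up". Its efficacy criterion names cardiac MRI and neurologic MRI at 3 months. In Attachment II, echocardiograms and neurological imaging occur only at weeks 0 and 24.

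**The concern.** An open-label drug prevents masking of patients and treating staff. It does not prevent masking of someone measuring stored images. Because everyone is treated, there is no allocation to hide from a reader. What could influence the measurement is knowing which scan came before treatment and which after.

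If that knowledge moves readings slightly in one direction, the paired analysis counts the movement as change on treatment. A randomised comparison with masked readers would tend to cancel such a shift; this design has no second arm in which it could cancel. The false discovery rate p-values in Section 7.2 do not help, since they deal with chance findings and not with bias. One reader's tendency could also move several correlated measures together and look like consistent evidence.

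**Working it through.** **Inputs**

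- n = 10 patients; paired t-test; two-sided 5% level; effect size 1 SD; stated power 80% (Sections 7 and 7.1).
- Target of ten completers, with withdrawn subjects replaced (Section 4.5).
- Reader shift b, in SDs of the within-patient change: **assumed**. The documents give no reader shift and no imaging SD; the only SD is 234.3, for BNP (Section 7.1).

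**Step 1: the plan's own figure.** The paired t statistic has df = n − 1 = 9 and noncentrality d × √n. The critical value is t(0.975, 9) = 2.262. At d = 1 the noncentrality is √10 = 3.162 and power is 80.3%. The stated 80% reproduces.

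**Step 2: the same formula with no drug effect and a reading shift.** Put d = b and take the upper tail, P(T > 2.262), the chance of a significant result in the direction of improvement.

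| Assumed shift b (SD) | Noncentrality b × √10 | False significant improvement |
|---|---|---|
| 0 | 0 | 2.5% |
| 0.05 | 0.158 | 3.5% |
| 0.1 | 0.316 | 4.7% |
| 0.25 | 0.791 | 10.6% |
| 0.5 | 1.581 | 29.3% |

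These figures apply to one endpoint. Counting both directions, the total rejection rate goes from 5.0% with no shift to 10.9% at 0.25 SD and 29.3% at 0.5 SD. Masked reading leaves n and stated power unchanged; what it protects is the error rate.

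**Step 3: which reads can wait.**

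| Imaging | Scheduled (Attachment II) | Needed before study end? |
|---|---|---|
| Echocardiogram | Weeks 0, 24 | Not for dosing; not named in the interim criterion |
| Spinal cord and cerebellar MRI | Weeks 0, 24 | Not for dosing; the interim criterion names neurologic MRI at 3 months, but none is scheduled then |
| Cardiac MRI | Weeks 0, 12, 24 | Baseline and week 12 are needed for the dose decision and the interim look |

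A batch read at study end therefore fits the first two rows directly. For cardiac MRI it can only be an additional read: 10 patients × 3 visits = 30 scans.

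**Step 4: would removing dates mask the visit?** Not fully. The Visit 3 text names a compact 3T scanner for cerebellar MRI and the baseline text does not. Perfusion MRI is done at weeks 0 and 24 but not at week 12. Either feature could reveal the visit.

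**The case against.** **Silence is not proof of unmasked reading.** A reader might infer from Section 5.7 that readers will know the visit. The documents do not support that. The section sits among drug-handling provisions, gives the medication as its only reason and does not mention readers. What stands is that no reader masking is specified, so a team following the plan has no instruction to mask.

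**Nor is manual contouring described.** A reader might assume every imaging measure is hand-drawn and equally open to influence. The protocol does not state the degree of automation for any of them. Susceptibility is unknown and probably varies between measures.

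**The magnitude is hypothetical.** This stands. The calculation shows how sensitive the test is to a shift; it is not evidence that a shift will occur. At the low end the effect is small: 3.5% against 2.5%. Extending the range upward gives more striking numbers (56.2% at 0.75 SD), but nothing in the documents supports a shift of that size.

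**One batch read cannot replace all live reads.** Correct for cardiac MRI, where baseline and week-12 results are used during the trial. A reader who made those live reads may also recognise scans from only 10 patients, so masking would be partial if the same person re-reads them.

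**The benefit is limited.** FARS is rated in person and is untouched. Regression to the mean, practice effects and the lack of a control arm remain, and the power calculation rests on BNP, a blood marker. This bounds what masking achieves; it is no reason to leave an avoidable bias in the imaging endpoints.

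**Conclusion.** The concern holds in this form: the plan specifies no masking of image readers, and its stated reason, open-label drug, does not rule such masking out. The gap affects primary endpoints in a single-arm before-after comparison, where a systematic reading shift would be indistinguishable from a drug effect.

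The size cannot be established from the documents. The illustrative range, 3.5% to 29.3% against a nominal 2.5%, rests on assumed shifts of 0.05 to 0.5 SD, n = 10, no true effect and a paired t-test on a single endpoint. The change should be made because it is cheap and removes an ambiguity that cannot be resolved after the fact. The trial can proceed otherwise unchanged.

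**What to change.** Amend Section 5.7 to state that the drug is open label and that endpoint image reading is masked to visit, as follows.

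1. **Echocardiogram and spinal cord and cerebellar MRI.** Existing readers make the endpoint measurements in one batch at study end, with dates and visit labels removed and scans in random order.
2. **Cardiac MRI.** Keep the live baseline and week-12 reads for their current dosing and interim uses. Take the efficacy values from a separate masked, random-order read at study end, assigned where possible to an existing reader who did not make that patient's live reads. State in Section 7.2 that this read supplies the analysis values.
3. **Visit cues.** Match or remove them: the scanner used for cerebellar MRI, and the perfusion sequences that are absent at week 12.
4. **Reconcile Section 7.2 with Attachment II.** The interim criterion uses neurologic MRI at 3 months and none is scheduled then. If resolving this creates a live use for neurologic MRI, the split in item 2 would be needed there too.

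The cost is about 30 cardiac MRI re-reads and a later date for the echocardiogram and neurological measurements. No patients, visits or scans are added. Some recall will remain if the same readers must be used. FARS, regression to the mean and practice effects are not addressed and should be acknowledged as limitations.

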5.8 Receiving, Storage, Dispensing and Return of Study Medication

5.8.1 Receipt of Drug Supplies

The Mayo Clinic Research Pharmacy will maintain drug shipment and dispensing accountability records, including shipping receipts/packing slips for incoming shipments of (+) EPI and dates/number of capsules/bottles and the lot numbers dispensed to subjects.

Expiry dating/retest dates will be provided by Cardero Therapeutics, based on ongoing stability testing. Documentation of expiry/re-test dates will be retained with study records.

Subject dosing/AE diaries will be provided to the subject/LAR by the study team with completion instructions. Subjects will be asked to bring their completed diaries back to the site, with any full or partial bottles to facilitate reconciliation.

The quantity of capsules dispensed, taken, returned or discarded by the subject will be reconciled by the study team during visits to determine compliance with the prescribed dosing regimen.

Study drug reconciliation will be documented in study records.

5.8.2 Storage Conditions

Capsules will be stored in HDPE bottles as packaged by Syngene, and maintained at 2 to 8 degree storage within the Mayo Clinic Research Pharmacy. Subjects/LAR will be advised to keep bottles refrigerated in their homes.

